## **15.0 END OF STUDY CRITERIA**

After 4-6 weeks of treatment, patients will stop study treatment and after all 100 subjects have been randomized, enrollment will be closed. The study will be considered terminated when the 100th patient has made the follow-up visit.

### **15.1 Premature discontinuation**

Subjects who, for various reasons, do not complete the treatment period will be classified as having dropped out of the study early.

Some possible reasons for early exit include:

- Inappropriate recruitment;
- Adverse event;
- Personal reasons: a patient may withdraw from the study at any time and for any reason.

## **16.0 TOXICITY MONITORING AND ADVERSE EVENT MANAGEMENT**

### **16.1 Adverse Event Definitions**

Adverse event (AE): is any undesirable medical event in a patient or subject included in a clinical trial and which does not necessarily have a causal relationship with the treatment.

Serious adverse event (SAE) or serious adverse reaction (SAR) or suspected unexpected serious adverse reaction (SUSAR): any adverse event or adverse reaction that, regardless of dose, results in death or is life-threatening, requires hospitalisation or prolongation of hospitalisation, or results in severe or prolonged disability or incapacity, or involves a congenital anomaly or birth defect.

### **16.2 Adverse Event (AE) and Serious Adverse Events (SAE) Reporting**

All AEs must be recorded in the appropriate section of the CRF, regardless of whether or not they are directly related to the study treatment.

All SAEs and SUSARs must be reported on a specific form provided by the coordinating center and processed in the following manner:

SAE and SUSAR. Each investigator will ensure that all information relating to SAE is recorded on the appropriate phytovigilance form and notified to the Coordinating Centre within 24 hours of the first knowledge of the SAE by the responsible investigator ([contact]; [contact]), and that subsequent relevant information is communicated within eight days of

the first report. The Coordinating Centre will be responsible for sending reports of suspected reactions to the study treatment to the Istituto Superiore di Sanità.

Once a year, the principal investigator will provide the Ethics Committees with a list of all SAEs and SUSARs observed throughout the entire period.

The occurrence of CCR will not be considered as a SAE.

## **17.0 STATISTICAL METHODS**

### **17.1 Statistical design and sample calculation**

The primary endpoint of the study is the difference in  $\beta$ -catenin values [post-treatment value - pre-treatment value].

Data from our previous trial on the same study population (APAC Study) allow us to make some assumptions: we assume a baseline mean of  $\beta$ -catenin expression in adenomatous tissue equal to 25% (standard deviation=35) and a correlation between baseline and final  $\beta$ -catenin values equal to approximately 0.9. Given these assumptions, using an ANCOVA model (therefore adjusting the analysis for baseline  $\beta$ -catenin values), with 50 subjects per arm, for a total of 100 subjects, we will have an 85% power to observe a mean difference between the two arms equal to 10%, in the levels of  $\beta$ -catenin expression in adenomatous tissue. The sample calculation takes into account 10% of subjects lost to follow-up and a 2-tailed alpha error equal to 5%.

### **17.2 Interim analysis**

At approximately halfway through the study, which will approximately coincide with 50% of enrolled patients completing treatment, the study monitoring committee, composed of the principal investigators from each center, the biostatistician, and the study coordinator, will perform an interim analysis to assess any adverse and/or toxic effect of the active treatment compared to placebo. This analysis will therefore consider 2 endpoints in the comparison arms: 1) number of adverse events 2) size of the adenoma.

With a total of n=50 subjects, there will be sufficient power to detect an absolute difference of 40% in terms of frequency of adverse events and in terms of change in size of the adenoma between the active arm and placebo at the end of treatment (assuming an ANCOVA model corrected for baseline size and a correlation coefficient of 0.7 between mean baseline and final size). In case of a significantly greater adverse and/or toxic effect in the active arm, the monitoring committee will consider the possibility of prematurely stopping the study.

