### **9.2 Secondary objectives**

1. Evaluate the effects of treatment on:

- oxidative stress and inflammation through the evaluation of IHC expression changes of Nuclear Factor-K $\beta$  (NFK $\beta$ ), one of the major transcription factors involved in the regulation of normal and neoplastic cells, closely related to the inflammatory and carcinogenic pathways of colon cancer;
- cell proliferation (Ki-67 labeling index), P53 mutation, tissue gene expression with microarray;
- circulating growth factors of the IGF system (IGF-I, IGFBP-3 and IGF-I/IGFBP-3) and EGFR;
- markers of inflammation (u-PCR).

2. Evaluate the tolerability of the treatment, as a combination of 2 food supplements and study the plasma and possibly tissue absorption of the active ingredients present in the botanical extracts (anthocyanosides and curcumin) .

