### **17.3 Statistical analysis methods**

All subjects enrolled in the study will be considered in the “Intention To Treat” (ITT) population, and the statistical analysis will be performed in accordance with this principle, therefore considering the randomized subjects regardless of their actual adherence to the experimental treatment.

The descriptive statistics used for continuous variables will be: mean, standard deviation, median, quartiles, minimum and maximum; for discrete variables they will be: absolute frequency and relative frequency.

In agreement with previous results, the difference in post- and pre-treatment values of  $\beta$ -catenin [post-treatment value - pre-treatment value] is a normally distributed variable. However, the normality of the distribution will be tested and, if necessary, the necessary transformations will be applied to obtain normality.

Fisher's exact test and chi-square test will be used to compare proportions in the two treatment arms (toxicity: number of adverse events), while parametric (t-test) and non-parametric (Mann-Whitney U) tests will be used to compare continuous variables.

Parametric statistics will be used for the primary objective. Hypotheses will be tested using the general linear model: the null hypothesis of no treatment effect will be tested using standard analysis of variance (ANOVA) and covariance (ANCOVA) methods, adjusting for baseline  $\beta$ -catenin and the effect of other possible confounding factors such as age, sex, body mass index (BMI), family history of colon cancer, smoking habits, alcohol consumption and other important factors (demographic and/or biological) collected.

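### The only planned toxicity comparison between arms pools all adverse events; severity grading and a by-arm comparison of serious events are not specified, so a shift towards worse events can be missed

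*Combined protocol and SAP*

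**What the plan says.** Section 17.2 plans an "interim analysis to assess any adverse and/or toxic effect of the active treatment compared to placebo" when about half the patients have completed treatment. It then names what is compared: "This analysis will therefore consider 2 endpoints in the comparison arms: 1) number of adverse events 2) size of the adenoma". The first is the only toxicity measure. Its size is justified by "With a total of n=50 subjects, there will be sufficient power to detect an absolute difference of 40% in terms of frequency of adverse events"; no control rate and no numerical power are given. The consequence, a possible early end of the trial, is advisory ("In case of a significantly greater adverse and/or toxic effect in the active arm, the monitoring committee will consider the possibility of prematurely stopping the" [...]). That sentence sets no criterion for seriousness or severity.

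Section 17.3 assigns Fisher's exact and chi-square tests to the final comparison ("toxicity: number of adverse events"). Tolerability is a secondary objective in section 9.2 ("Evaluate the tolerability of the treatment"), and no other metric is defined for it.

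Section 16.1 defines adverse events and serious adverse events. Section 16.2 has every adverse event recorded whether or not it is related to treatment. It sends each SAE to the coordinating center within 24 hours and has the principal investigator, once a year, "provide the Ethics Committees with a list of all SAEs and SUSARs". Section 10.5 allows a single subject's code to be revealed after a serious event that may be related. None of these sections mentions a severity grade or a comparison of serious events by arm.

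**The concern.** The interim look exists to find a greater adverse or toxic effect in the active arm. A measure that pools all events gives a minor complaint the same weight as a hospitalisation. If the supplements make events worse without making them much more frequent, the pooled comparison has little to detect. The same applies at the end of the trial. Section 11.5 also collects adverse events one year after a treatment of 4 to 6 weeks; if those enter the final count, they add background events.

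At stake are the committee's advisory assessment and the tolerability conclusion. Either could report no difference in adverse events while serious or severe events differ between arms. The primary beta-catenin analysis is not affected.

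**Working it through.** **Inputs from the documents.** Interim n = 50 in total (17.2); 50 per arm at the end and 10% loss, so about 45 per arm (17.1); interim difference of 40 percentage points (17.2).

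**Assumptions.** 25 per arm at the interim, from the equal arms planned in 17.1. Two-sided 5% for the adverse-event tests, which 17.1 states only for the primary endpoint. Subjects, not events, as the unit, because Fisher and chi-square tests compare proportions of subjects. All event rates below.

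**The plan's own figure.** The pooled normal approximation is

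power = Φ{[d − 1.96·√(2p̄(1−p̄)/n)] / √([p₁(1−p₁)+p₂(1−p₂)]/n)}.

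The least favourable case for a 40-point difference is 30% v 70%, with n = 25 and p̄ = 0.5:
- 1.96·√(0.5/25) = 0.277
- √(0.42/25) = 0.130
- (0.400 − 0.277)/0.130 ≈ 0.95, so power is 83%.

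At 0% v 40% it is 97%. By exact Fisher enumeration the range is 78% to 97%. The claim of sufficient power for 40 points therefore holds if it means about 80%. It concerns any-event frequency only.

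**Power to flag harm.** For n per arm, sum Bin(i; n, p_placebo)·Bin(j; n, p_active) over all tables with j > i and two-sided Fisher p ≤ 0.05. The first three rows are the planned test when severe or serious events occur in 23% v 3% of subjects. They differ in how much of that 20-point excess also raises the any-event rate.

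| Comparison (active v placebo) | 25 per arm | 45 per arm | 50 per arm |
|---|---|---|---|
| Any event, 50% v 50% (none adds) | 1.6% | 1.3% | 1.8% |
| Any event, 60% v 50% (half adds) | 7.5% | 10% | 13% |
| Any event, 70% v 50% (all adds) | 23% | 41% | 46% |
| Severe or serious, 23% v 3% | 39% | 78% | 81% |
| Severe or serious, 10% v 2% | 2.3% | 15% | 19% |

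With other assumed rates (any event 40% in both arms, severe or serious 20% v 2%), the planned test gives 1.5% at 25 and 1.6% at 50 per arm. The direct comparison gives 30% and 78%. If all 18 points add (58% v 40%), the planned test gives 20% and 38%.

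**What one interim table would show.** With 25 per arm and no serious events on placebo:
- 6 v 0: p = 2·C(25,6)/C(50,6) = 2 × 177,100/15,890,700 = 0.022.
- 5 v 0: p = 2·C(25,5)/C(50,5) = 2 × 53,130/2,118,760 = 0.0502.
- Alongside either, 14 v 13 subjects with any event gives p = 1.0.

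A 6 v 0 split would thus be invisible in the pooled comparison, but nothing smaller than 6 v 0 reaches 5% even when tested directly.

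**The case against.** A reader might infer that serious events are hidden from the committee, or that it never sees them. The documents do not support that. Section 16.2 brings each SAE to the coordinating center within 24 hours. The committee in 17.2 includes the centers' principal investigators and the biostatistician, and 10.5 allows individual unblinding. The stated purpose is broad and the stopping language advisory, so nothing bars the committee from weighing SAE reports it already has. What stands is narrower: no planned analysis sets these events side by side by arm, and 17.2 names its two endpoints explicitly. Severe events that are not serious have no separate route in the protocol.

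A reader might also infer that the pooled test has almost no sensitivity. That is true only if the extra severe events fall on subjects who would have had an event anyway. If the full excess adds to the any-event rate, power is 23% and 46%: lower than the direct comparison's, but not negligible.

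A 20-point excess is large for food supplements that sections 6.1 and 10.2 describe as well tolerated. For 10% v 2% the direct comparison is itself weak. That limits the value of a significance test at the interim, but not of the tabulation.

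Finally, the case report form (CRF) is not among the documents. A severity field may exist there; the supportable statement is that the protocol does not specify grading.

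**Conclusion.** The concern holds as a gap in the planned comparisons. Sections 17.2 and 17.3 rest the between-arm toxicity assessment on all adverse events pooled. The protocol specifies neither severity grading nor a comparison of serious events by arm.

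For an assumed 20-point excess in severe or serious events, the planned test flags harm with 1.6% to 23% at the interim, against 39% for a direct comparison. At 50 per arm it is 1.8% to 46%, against 81%. These figures depend on assumed event rates, subject-level analysis and a two-sided 5% level. Even the direct comparison misses that excess at the interim 61% of the time. The gain there is that the committee sees the counts by arm; the gain in power is mainly at the final analysis. The change should be made, but it concerns safety reporting in a small trial with an advisory look and does not affect the primary result.

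**What to change.** - **Section 17.2:** add to the interim report, by arm, the number of subjects with at least one SAE and with at least one severe adverse event, each with the between-arm difference and an exact 95% confidence interval. Keep the two existing endpoints and the advisory wording.
- **Section 17.3:** add worst severity per subject and subjects with at least one SAE, by arm. State the Fisher or chi-square comparison as subjects with at least one adverse event, since those tests do not compare counts of events.
- **Section 16.2:** require each adverse event to be graded on a named standard toxicity scale, and add the CRF field if it is not already there.

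The cost is small: at most one CRF field, a few table rows and wording in three sections. SAEs are already collected centrally. The downside is one or two more safety comparisons, hence a slightly higher chance of a false alarm in an advisory look. The alpha for beta-catenin is unaffected.

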### **17.3 Statistical analysis methods**

All subjects enrolled in the study will be considered in the “Intention To Treat” (ITT) population, and the statistical analysis will be performed in accordance with this principle, therefore considering the randomized subjects regardless of their actual adherence to the experimental treatment.

The descriptive statistics used for continuous variables will be: mean, standard deviation, median, quartiles, minimum and maximum; for discrete variables they will be: absolute frequency and relative frequency.

In agreement with previous results, the difference in post- and pre-treatment values of  $\beta$ -catenin [post-treatment value - pre-treatment value] is a normally distributed variable. However, the normality of the distribution will be tested and, if necessary, the necessary transformations will be applied to obtain normality.

Fisher's exact test and chi-square test will be used to compare proportions in the two treatment arms (toxicity: number of adverse events), while parametric (t-test) and non-parametric (Mann-Whitney U) tests will be used to compare continuous variables.

Parametric statistics will be used for the primary objective. Hypotheses will be tested using the general linear model: the null hypothesis of no treatment effect will be tested using standard analysis of variance (ANOVA) and covariance (ANCOVA) methods, adjusting for baseline  $\beta$ -catenin and the effect of other possible confounding factors such as age, sex, body mass index (BMI), family history of colon cancer, smoking habits, alcohol consumption and other important factors (demographic and/or biological) collected.

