### **10.5 Treatment assignment method**

All eligible patients after signing the informed consent must be randomized before starting study treatment. Randomization will be centralized at the Medical Oncology Department of the EO Ospedali Galliera through a computerized procedure. The randomization list will be prepared by the biostatistician of the Scientific Coordination Office of the coordinating center independently: permutation blocks of different sizes will be used, stratified for the enrolling sites. Randomization will be performed using a paper form sent by FAX to the Medical Oncology Department at Galliera Hospital. Once it is ascertained that the form has been filled out correctly, a patient ID corresponding to the kit will be associated with the eligible patient.

An operating manual for randomization of study subjects will be provided to centers.

Subjects will be randomized in a strictly sequentially sequenced manner and will remain in their assigned arm for the duration of the study.

The procedure for assigning treatment to randomized subjects will be kept blind according to the following method: the supplement packages (Mirtoselect® 500 mg, Meriva® 500 mg, placebo A, B) will be prepared in blisters containing 90 identical tablets, supplement and reference placebo, in order to allow for masking. Each pack will contain 10 blisters of 9 tablets for each individual product (supplement or placebo). For treatment, each subject will receive a “patient kit”, i.e. a box containing a pack of Mirtoselect® + a pack of Meriva®, or a pack of Placebo A + a pack of Placebo B. Each “patient kit” box will be associated with the subject using the code indicated in the randomization list. The preparation of the supplements will be carried out according to good practices for preparing botanical extracts and will be paid for by Indena SpA. Indena will identify an operator responsible for receiving the open-label (unmasked) randomization lists from the statistician, who will archive the lists for any future checks. The treatment code may be revealed to the clinician and the patient only at the end of the study or if it is necessary following a serious adverse event that could be related to the experimental treatment or in any case in cases where, for medical emergencies, it is necessary to know the treatment associated with the subject in the study.

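### Should the open-ended rule to test the β-catenin difference for normality and transform it be replaced by a fixed raw-scale analysis?

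*Combined protocol and SAP*

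**What the plan says.** Section 17.1 sets the endpoint on the raw scale: "The primary endpoint of the study is the difference in" β-catenin values, post-treatment minus pre-treatment. Its planning values are β-catenin "expression in adenomatous tissue equal to 25% (standard deviation=35) and a correlation between baseline and final" values of about 0.9. With ANCOVA, 50 subjects per arm, 10% lost to follow-up and two-sided alpha of 5%, it states that "we will have an 85% power to observe a mean difference between the two arms equal to 10" percent.

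Section 17.3 says that, in line with previous results, the difference "post-treatment value - pre-treatment value] is a normally distributed variable". The next sentence is the contingency: "However, the normality of the distribution will be tested and, if necessary, the necessary transformations will be applied to obtain normality". The section then says "Parametric statistics will be used for the primary objective", by ANOVA and ANCOVA adjusted for baseline β-catenin and "the effect of other possible confounding factors such as age, sex, body mass index (BMI") and others.

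No section names the normality test, its threshold, whether arms are pooled, or the transformation. Nor does any section say whether the difference itself is transformed, or the pre and post values are transformed and then subtracted.

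**The concern.** Because the primary analysis stays parametric, a failed normality test changes its scale. Three things would follow. The primary result would no longer be a difference in percentage points. The 85% would no longer describe the test performed. The scale would be settled after the data exist.

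There is also a practical snag. A difference can be negative, so a plain log or square root cannot be applied to it, and the analyst must choose how to proceed.

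The planning values add to the worry. If the score runs from 0 to 100 (an assumption), a mean of 25 with SD 35 means strongly skewed baseline values. A treatment effect that depends on baseline can also make the pooled difference non-normal, so the effect under test could itself trigger the switch. If the choice of scale often decided the result, the trial's single primary comparison would be open.

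**Working it through.** **1. The plan's own figure.** Inputs from section 17.1: SD 35, correlation 0.9, difference 10, 50 per arm less 10% = 45 per arm, two-sided 5%. The final SD is assumed to equal the baseline SD.

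- Change score: SD = 35 × √(2 × (1 − 0.9)) = 15.65; standard error = 15.65 × √(2/45) = 3.30; 10/3.30 = 3.03; noncentral t on 88 df gives **85.0%**.
- ANCOVA: residual SD = 35 × √(1 − 0.9²) = 15.26; standard error = 3.22; 10/3.22 = 3.11; noncentral t on 87 df gives **86.8%**.

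The stated 85% is right, with the 10 read as raw percentage points.

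**2. How often the rule would fire.** Shapiro-Wilk at 5% on the pooled difference, 45 per arm (all assumed):

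| Assumed data | Rule fires |
|---|---|
| Difference exactly normal, no effect or pure 10-point shift | about 5% |
| Bivariate normal (mean 25, SD 35, r 0.9), active final values × 0.6 | 7.5% |
| Difference normal, another assumed link of baseline to final values, proportional or floored fall | 49-52% |
| Three skewed 0-100 shapes | 100% |

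The last row contradicts the plan's statement that the difference is normal. Among the rows consistent with it, the range is about 5% to about 50%. It depends on a joint distribution that the documents do not give.

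**3. Type I error.** Raw-scale ANCOVA gave 4.2-5.5%. Switching to any one of eight transformations when the test failed gave 3.5-5.3%. Transforming until the test passed, in three skewed shapes (3,000 null trials), gave 4.6-5.6%. Error rises only if the scale is picked by its p-value: 7-9% for the best of five scales, and 10.9% in another set of five. Section 17.3 makes normality the criterion, not the result.

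**4. Power when the rule is followed as written.** The transformation must *obtain normality*. In a skewed Beta shape (mean 25, SD 35), applying log(x+1) to pre and post values gave low power for a proportional fall, about 43-50% depending on the exact correlation. But log, square-root and arcsine scales reached normality in only 0-0.4% of trials, so that loss does not come from the plan's rule. Rank-based normal scores of the difference did reach it: power was 81-85% against raw 92-94% for a proportional fall, and 99% against raw 90% for a floored fall.

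Transforming until normal, in three skewed shapes with a mean difference of about 10 (700 trials per setting):

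| Effect | Raw scale | Transform until normal |
|---|---|---|
| Active final values × 0.6 | 92-93% | 78-95% |
| Fixed fall, floored at 0 | 87-92% | 96-100% |

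**5. The alternative.** Holding to the raw scale avoids a loss of at most 93 − 78 = 15 points in the first row. It gives up about 10 points in the second. In a separate run of one shape with 20 points subtracted, raw ANCOVA had 84.6% power and the arcsine scale 98.2%, a gap of 13.6 points.

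**The case for a change.** The strongest case for a change is that the sentence governs the one primary comparison, that the choice is open, and that closing it costs a line of text. A fixed raw-scale ANCOVA keeps the endpoint, the 10 points and the 85% together, and it held its type I error in every shape tried, so the transformation is not needed for validity. Applying the check to ANCOVA residuals would not remove the issue: where the difference was normal but the effect depended on baseline, residuals still failed in 17-40% of trials.

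Much of this stands. The plan would read better with the test and transformation named, and if the rule fires, the stated power does not carry over to the new scale.

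Three parts do not carry the case. First, frequent firing rests on shapes that contradict the plan, or on a link between baseline and final values that it does not give. Second, the largest power losses come from transformations that fail the plan's own criterion. Third, the raw scale is one of two reasonable remedies. Naming one test and one transformation would close the gap equally well, although it would need an effect size and power on that scale. Neither choice is better across the shapes tried.

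The raw scale would not vanish from the report either. Section 17.3 already lists means, standard deviations, medians and quartiles for continuous variables, so the change in percentage points can be shown by arm whatever scale is tested.

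**Conclusion.** No change is needed. This is missing detail combined with a fair trade-off, not a wrong number. The 85% reproduces on the scale for which it is stated, and the rule as written still gives a valid test, with type I error of 4.6-5.6% in the shapes tried. Following it would cost up to about 15 points of power if the fall is proportional, and gain about 10-14 points if the fall is floored at zero. If the difference is normal, as section 17.3 asserts, the rule fires in about 5% of trials with no effect or a pure shift, and in about 7.5% to 50% when the effect depends on baseline.

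All simulated figures rest on assumed shapes, a Shapiro-Wilk test at 5% and 45 evaluable per arm. They show sensitivity and are not estimates for this trial. The conclusion also assumes that the scale is chosen for normality and not for its p-value. An analyst can meet that condition by checking the pooled difference without treatment labels and recording the scale before unblinding.

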**SECONDARY OBJECTIVES**

- Evaluate the tolerability of the combination of blueberry extract and turmeric extract and study the plasma and tissue absorption of the active ingredients (anthocyanosides and curcumin);
- Evaluate the effects of treatment in the adjacent adenomatous and healthy tissue (perilesional) by evaluating the IHC expression of Nuclear Factor-K $\beta$  (NFK $\beta$ ), Ki-67, P53 apoptosis, tissue expression of the EGFRs system; tissue gene expression;
- Evaluate the modulation of some circulating growth factors in the collected serum: IGF system (IGF-I, IGFBP-3 and IGF-I/IGFBP-3), EGFR, inflammation markers (u-PCR).

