## 7.0 STUDY DESIGN

Randomized, preoperative, double-blind, placebo-controlled study.

*Randomized, double-blind, placebo controlled study*

Subjects with polyp of probable colorectal adenomatous nature will undergo biopsy of the polyp and healthy perilesional tissue during colonoscopy. After histological confirmation of AP and eligibility criteria verification, patients will be randomized to one of the two treatment groups. After four weeks of treatment, the second colonoscopy with polyp removal and biopsy of healthy perilesional tissue will be performed. The biopsy of the healthy tissue will be performed in the rectum if there is macroscopic inflammation in the sigma; in the absence of inflammation, it will be performed in the sigma.

The determination of tissue biomarkers to verify the study hypotheses will be performed on adenomatous and normal tissue from adenoma biopsy taken at baseline and on the removed polyp and on the normal tissue biopsy after 4 weeks of treatment. Circulating biomarkers will be measured at baseline and at the end of treatment.

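### Section 17.3 does not fix how the continuous secondary biomarkers are compared (final value or change, which test, baseline-adjusted or not); ANCOVA on each marker's own baseline would settle it and gain precision at no cost

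*Combined protocol and SAP*

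**What the plan says.** Section 17.3 gives one general rule for measurements: "while parametric (t-test) and non-parametric (Mann-Whitney U) tests will be used to compare continuous variables". It does not name the response (final value or change) or say when each test applies.

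The next paragraph of 17.3 opens "Parametric statistics will be used for the primary objective" and continues "Hypotheses will be tested using the general linear model". It describes ANOVA and ANCOVA adjusted for baseline β-catenin and a list of possible confounders, ending with "other important factors (demographic and/or biological) collected". No other marker's baseline is named. Post minus pre is defined as a response only for β-catenin (17.1 and 17.3), and the normality check with possible transformation is also described only for that difference.

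The secondary objectives are worded in terms of change. The synopsis has "Evaluate the modulation of some circulating growth factors in the collected serum", and section 9.2 addresses oxidative stress and inflammation "through the evaluation of IHC expression changes of Nuclear Factor-K" (the quote stops at the Greek letter in the marker's name).

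Section 7.0 provides for both time points. For blood: "Circulating biomarkers will be measured at baseline and at the end of treatment". Tissue determinations "will be performed on adenomatous and normal tissue from adenoma biopsy taken at baseline and on the removed polyp", and also on the normal-tissue biopsy taken after treatment.

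**The concern.** Two analysts working from 17.3 could analyse the same secondary marker differently: a t-test on final values, a t-test on changes, a Mann-Whitney test on either, or ANCOVA. The text does not exclude any of these.

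This has two consequences. First, precision: if the unadjusted tests are used, information in the baseline measurement is partly lost (change scores) or wholly lost (final values), although that measurement has already been paid for. Second, with two tests named and no rule between them, the choice could follow the data and the nominal 5% error rate would no longer hold exactly.

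The secondary markers are a main source of mechanistic evidence in a phase II biomarker study, so this is worth settling. The point covers secondary biomarkers measured on a continuous scale. Microarray gene expression, P53 mutation, tolerability and plasma absorption are outside it.

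**Working it through.** **The plan's own figure.** Section 17.1 gives SD 35, ρ about 0.9, a difference of 10, 50 per arm with 10% lost (45 evaluable), two-sided 5% and 85% power.

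- ANCOVA: residual SD = 35·√(1−0.9²) = 15.26; noncentral t with 87 df gives 86.8%.
- t-test on change: SD = 35·√(2(1−0.9)) = 15.65; noncentral t with 88 df gives 85.0%.
- t-test on final values: SD 35; about 27%.

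The stated 85% is reproduced, to within two points by ANCOVA and exactly by a change-score test. With the same inputs, ignoring the baseline would be very costly. The response therefore has to be stated.

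**Secondary markers: formulas.** Assume equal variances σ² at both times and correlation ρ. The variance per subject is:

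- final value: σ²
- change: 2(1−ρ)σ²
- ANCOVA: (1−ρ²)σ²

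Information lost relative to ANCOVA:

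- change: 1 − (1−ρ²)/(2(1−ρ)) = (1−ρ)/2
- final value: 1 − (1−ρ²) = ρ²

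**Numbers.** The documents give no ρ, SD or effect for any secondary marker. The range of ρ and the 0.5 SD effect below are assumptions. The plan uses 0.9 (β-catenin, 17.1) and 0.7 (adenoma size, 17.2) for other variables. Power is from the noncentral t with 45 per arm and two-sided 5%.

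| ρ | Variance, change (σ²) | Variance, ANCOVA (σ²) | Loss, change | Loss, final value | Power, t-test on change | Power, ANCOVA |
|---|---|---|---|---|---|---|
| 0.3 | 1.40 | 0.91 | 35% | 9% | 51% | 69% |
| 0.5 | 1.00 | 0.75 | 25% | 25% | 65% | 77% |
| 0.7 | 0.60 | 0.51 | 15% | 49% | 86% | 91% |
| 0.9 | 0.20 | 0.19 | 5% | 81% | >99% | >99% |

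A t-test on final values has about 65% power at every ρ. In sample-size terms, 45 per arm analysed as changes is worth 45(1+ρ)/2 per arm under ANCOVA: 29, 34, 38 and 43 down the table. For an assumed 0.3 SD effect, change versus ANCOVA is 22 vs 31%, 29 vs 37%, 44 vs 50% and 88 vs 90%.

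**Free choice of test.** Null simulation, 45 per arm, ρ from 0.3 to 0.9, 20,000 runs per setting, taking the smaller of the t-test and Mann-Whitney p-values on change:

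- normal data: 5.8–6.2% false positives
- lognormal, σ = 0.5: 6.4–6.8%
- lognormal, σ = 1: 6.9–7.2%

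A smaller run (3,000 per setting) gave 5.8–7.9%. About 6–8% is a fair summary.

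**The case against.** Five points can be made on the other side.

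1. *The general linear model may already cover these markers.* The plural in "Hypotheses will be tested using the general linear model", the open-ended covariate list, and the use of a variable's own baseline in 17.1 and 17.2 all allow that reading. It remains open, so a reader who infers that ANCOVA is ruled out for secondary markers goes too far. It does not settle the matter, however. The paragraph starts from the primary objective, its only named baseline marker is β-catenin, and the general rule for continuous variables still stands beside it.

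2. *The baseline is probably used anyway.* A reader might infer that the plan collects baselines and then ignores them. The documents do not support that. The objectives speak of modulation and change, and a t-test or Mann-Whitney test on change uses the baseline and is valid. What remains is a loss of precision and an unstated response.

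3. *The gain is small at the only correlations the plan uses.* This is true: 5% at 0.9 and 15% at 0.7. The larger gaps come from assumed values of 0.3 and 0.5.

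4. *Naming a parametric and a non-parametric test usually means choosing by distribution.* If that rule were followed, the error rate would stay near nominal: choosing by a Shapiro test on change at ρ = 0.7 gave 4.6–5.5% in simulation. The 6–8% needs deliberate picking. Rates of 10–14% arise only if the response scale is picked as well. The plan, however, states no rule for these markers.

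5. *Not every marker is known to be continuous.* This stands. The measurement scale of NFκB and of the tissue EGFR system is not given, and the recommendation has to be conditional on it.

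**Conclusion.** The point holds as a gap in specification with a cheap, more precise alternative. For the continuous secondary biomarkers, the only tests 17.3 clearly assigns are the t-test and Mann-Whitney U, without the response or the rule between them. Whether the baseline-adjusted model extends to these markers is unclear.

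If changes are compared, the information lost against ANCOVA is (1−ρ)/2: modest near ρ = 0.9 (5%), larger at 0.7 (15%), and material at 0.5 and 0.3 (25% and 35%). If final values are compared, the loss is ρ². These sizes rest on equal variances and on assumed correlations; the power figures also rest on an assumed 0.5 SD effect and 45 evaluable per arm.

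A reader might infer that the planned tests are invalid or that the trial's main result is at risk. Neither follows. Each named test is valid once fixed in advance, and the primary analysis and the sample size are not touched.

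**What to change.** Add to section 17.3:

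- Each secondary biomarker measured on a continuous scale is analysed by ANCOVA of the final value on arm and that marker's own baseline, reporting the adjusted difference with its 95% CI. Examples are Ki-67 labelling index, IGF-I, IGFBP-3, their ratio, circulating EGFR and u-PCR, plus NFκB and tissue EGFR if scored continuously. ANCOVA of the change on arm and baseline gives the identical treatment estimate on the same scale, so the wording of the objectives can stay.
- Tissue markers are analysed separately in adenomatous and healthy tissue, with the baseline from the same tissue. This needs stating because section 7.0 lets the healthy biopsy come from rectum or sigmoid depending on inflammation, so the site could differ between the two time points.
- Any transformation is fixed before unblinding.
- A rank-based analysis is sensitivity only, or the main analysis for markers scored in ordered categories.

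The cost is a short paragraph and minor programming. No new data, visits or subjects are needed.
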